7.5 Study documents: translations – reference language

- The protocol master document will be in English and French, all further language versions are translated thereof.
- The ICF master document will be in English and French, all further language versions are translated thereof.

8. Statistics

8.1 Definition of primary endpoint

T. trichiura infection status 14-21 days post-treatment assessed by Kato-Katz is the primary endpoint in our study.

8.2 Justification of number of trial subjects

The primary analysis of this trial aims to assess whether combined moxidectin and albendazole is more efficacious against *T. trichiura* infection compared to standard of care therapy (albendazole monotherapy). We estimate a true CR of 10% for albendazole monotherapy and 30% for combination moxidectin/albendazole against *T. trichiura*. We estimate that enrolling 85 participants per arm will be sufficient to identify a statistically significant difference with 90% power using a two-sided 5% significance level. Additionally, 85 individuals will be included for the ivermectin/albendazole treatment arm to re-evaluate the findings from a previous study with a surprisingly low CR of only 13%. This sample size would allow us to detect the smallest clinically important difference (as defined by our

study panel) of 15%-points with a power of about 75%. To account for a loss to follow-up of 10%, we anticipate to recruit 94 per arm = 282 participants in total.

The suggested sample size of a maximum eight PK samples from 14 willing adolescents (7 per concerned study arm) is sufficiently high to determine the population PK parameters and determine drug-drug interactions with a sparse sampling scheme.

8.3 Description of statistical methods

The primary analysis will be performed according to the intention-to-treat principles using the available case population, which includes all participants with any primary end point data. Subsequently, a per-protocol analysis will be performed. CRs will be calculated as the percentage of egg-positive participants at screening who become egg-negative after treatment. Differences among CRs will be assessed by using unadjusted logistic regressions.

EPG will be assessed by adding up the egg counts from the quadruplicate Kato-Katz thick smears and multiplying this number by a factor of six. The ERR will be calculated as:

$$ERR = 1 - \frac{\frac{1}{n} e^{\sum \log(EPG_{follow-up} + 1)} - 1}{\frac{1}{n} e^{\sum \log(EPG_{baseline} + 1)} - 1}$$

Geometric mean egg counts will be calculated for the different treatment arms before and after treatment to assess the corresponding ERRs. Bootstrap resampling method with 5,000 replicates will be used to calculate 95% confidence intervals (CIs) for ERRs and the difference between the ERRs.

Previously established nonlinear mixed-effects (NLME) models will be used to compare and determine pharmacokinetic parameters [33]. Concentrations are measured with a validated LC-MS/MS method [23, 26]. Using NLME, the key population PK parameters will be calculated based on which an effect on the drug-drug interaction will be determined:

- C_{max} maximal plasma concentration
- t_{max} time to reach C_{max}
- AUC area under the curve, from 0 to 24h and 0 to inf.
- $t_{1/2}$ elimination half-life

C_{max} and t_{max} will be observed values derived from the plasma concentration-time profile. Total drug exposure (AUC) and $t_{1/2}$ will be calculated with the NLME modeling software Monolix 2018R2 (Lixoft, Antony, France) using compartmental analysis. The elimination half-life will be estimated by the equation: $t_{1/2} = \ln 2 / \lambda$, where λ (the elimination rate constant) will be determined by performing a regression of the natural logarithm of the concentration values during the elimination period. Primary PK parameters including absorption rate (k_a), volume of distribution (V), and clearance (CL) will be estimated utilizing NLME modeling.

The exact design of the sparse sampling scheme will depend on the results of current PK trials of our group.

For the analysis of association between blood type and infection severity, frequency distributions and descriptive summary statistics of the data will be presented by blood type. Crude effect estimates will be presented and adjusted effect estimates will be calculated using uni- and multivariate logistic regression.

9. Duties of the investigator

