	
quadruple Kato Katz assays. Differences in CRs (between treatment arms) will be analyzed using logistic regression.
 
Geometric and arithmetic mean egg counts will be calculated for the different treatment arms before and after treatment to assess the corresponding ERRs. Bootstrap resampling with 5,000 replicates will be used to estimate 95% confidence intervals (CIs) for ERRs and differences between ERRs. Adverse events will be compiled into frequency tables and compared between treatment groups using descriptive summary statistics.
 
To determine popPK, PK/PD and drug-drug interaction parameters, nonlinear mixed-effects (NLME) modeling will be used.
 
The association between blood type and infection intensity will be analyzed using logistic regression. Microbial communities will be analyzed for within sample (alpha)-diversity (observed taxa, Shannon diversity, phylogenetic diversity, Berger-Parker dominance); between sample (beta)-diversity (Bray-Curtis dissimilarity, weighted and unweighted UniFrac distance), sample community composition (presence/absence and relative abundance of key taxa, most abundant taxon) and aggregate community composition (prevalence and relative abundance of key taxa, core microbiota).

GCP statement	This study will be conducted in compliance with the protocol, the current version of the Declaration of Helsinki, ICH-GCP E6 (R2) as well as all national legal and regulatory requirements.
Key explanation for the inclusion of children	This study will involve adolescents of at least 12 years of age, since an infection with T. trichiura occurs most often in children who are therefore the main target group of deworming campaigns. Younger children will not be included as moxidectin is registered only for children ≥ 12 years.
Recruitment procedure	
The trial will be conducted in Dabou and Jacqueville districts, Côte d'Ivoire.
 
It will take place in areas with moderate to high T. trichiura endemicity (communities with a prevalence $\geq 10\%$) identified from earlier studies and/or based on experience of the local collaborating team.

Coverage of damages	Winterthur, Police Nr. 4746321; L'Africaine des Assurances Côte d'Ivoire, Police Nr. 2020-12-8218320
Storage of data and samples for future research aims	After the study has been completed, all samples will be destroyed. Case report forms and electronic source data will be kept for a minimum of 20 years.

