4.3.1 Diagnosis

At screening, all participants will be asked to provide two stool samples. From each stool specimen, duplicate Kato-Katz thick smears (41.7 mg each) [18] will be prepared and read under a microscope for eggs of *T. trichiura*, *A. lumbricoides* and hookworm by experienced technicians. For quality control of *A. lumbricoides* and *T. trichiura* egg counts, 10% of slides will be re-read by another laboratory technician. Results are considered correct if the following tolerance margin is not exceeded: (i) No difference in presence/absence of *A. lumbricoides* and *T. trichiura* (ii) egg counts are +/-10 eggs for counts \leq 100 eggs or +/-20% for counts $>$ 100 eggs (for each species separately). In case discrepancies above the tolerance margin are noted in one or more slides, the respective slides are re-read by the local technicians. The new results are discussed, so that in case of discordant results, slides can be re-evaluated to reach consensus. All microscopically analyzed quadruplicate Kato-Katz thick smears will be destroyed after passing the quality control. The same diagnostic approach will be applied at 14-21 days after treatment.

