4.4 Measure to minimize bias

Study participants eligible for treatment will be randomly assigned to one of the three treatment arms using a computer-generated stratified randomization code. The random allocation sequence with block sizes that will be a multiple of 3 and stratified by 2 levels of infection intensity at screening (light: 1-999 EPG, and moderate plus heavy: ≥ 1000 EPG *T. trichiura* infections) will be provided by a statistician. This way, all treatment arms will have a similar proportion of participants with light infection intensity. Allocation concealment will be warranted using sequential, opaque, sealed envelopes. In the case of accidental unblinding or necessary code breaks, the sponsor will be immediately notified (within 24 hours) and data will be analyzed as set forth in section 8.3. Treatment arm A and B will be double blinded (*i.e.* study participants and the trial team/researchers conducting the treatment and assessing the outcomes will be blinded) using tablets and appearance-matched placebos in bottles relabeled with the respective arm (*i.e.* A or B) by investigators not involved in efficacy assessment of the trial. Treatment arm C (receiving ivermectin/albendazole) will be an open, unblinded group.

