5.2 Inclusion criteria

1. Aged between 12 and 60 years.

2. Written informed consent signed by either participant him/herself (18-60 years of age) or by parents/caregivers for underage adolescents (aged 12-17 years); and written assent by underage participant.
3. Agree to comply with study procedures, including provision of two stool samples at the beginning (screening) and at follow-up assessment 14-21 days after treatment.
4. Having at least two slides of the quadruple Kato-Katz thick smears positive for *T. trichiura* and infection intensities of at least 48 EPG.
5. Willing to be examined by a study physician prior to treatment.

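### Cure rates are compared without adjustment although every participant has a screening egg count; adjusting for log EPG would be a cheap improvement, not the correction of an error

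*Combined protocol and SAP*

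**What the plan says.** For the primary endpoint, section 8.3 fixes the model: "Differences among CRs will be assessed by using unadjusted logistic regressions". The synopsis is less specific: "Differences in CRs (between treatment arms) will be analyzed using logistic regression".

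The baseline value that could be used is complete by design. Section 4.3.1 says "At screening, all participants will be asked to provide two stool samples", and section 5.2 admits only people with "infection intensities of at least 48 EPG". Section 4.4 has the allocation "stratified by 2 levels of infection intensity at screening", with the cut at 1000 EPG.

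Planning is on the percentage-point scale. Section 8.2 says "We estimate a true CR of 10% for albendazole monotherapy and 30% for combination moxidectin/albendazole", and states that 85 per arm allows detection of a difference "of 15%-points with a power of about 75" per cent in connection with the ivermectin/albendazole arm. The only intervals named in section 8.3 are "95% confidence intervals (CIs) for ERRs and the difference between the ERRs". None is named for a CR, a CR difference or an odds ratio.

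**The concern.** The sponsor judged infection intensity important enough to balance by stratification, and then plans a comparison that discards it. If heavier infections are harder to cure, an adjusted analysis has more power at the same sample size. The gain would matter most for ivermectin/albendazole v albendazole, where the plan itself claims only about 75% power.

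A second, smaller gap sits beside it. Logistic regression yields an odds ratio, whereas the design targets and the smallest important difference are in percentage points. No interval on that scale is pre-specified, so it is not settled in advance how a reader will judge whether a 15-point difference is supported or excluded.

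**Working it through.** **1. The plan's own figures.** Inputs from section 8.2: n = 85 evaluable per arm, two-sided 5%. With d the difference and p̄ the mean of the two rates,

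power = Φ{ [d√n − 1.96·√(2p̄(1−p̄))] / √(p₁(1−p₁) + p₂(1−p₂)) }

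- 10% v 30%: (0.2 × 9.220 − 1.96 × 0.5657) / 0.5477 = 1.342, so power is 91.0%. The stated 90% reproduces.
- 10% v 25%: (0.15 × 9.220 − 1.96 × 0.5374) / 0.5268 = 0.626, so power is 73.4%, close to the stated figure of about 75%.
- 13% v 28%: (0.15 × 9.220 − 1.96 × 0.5709) / 0.5610 = 0.471, so power is 68.1%.

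Section 8.2 gives no base rate for the 15-point difference. The 10% is therefore an assumption, and the last line shows how much depends on it.

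**2. What is assumed for the gain.** The slope of cure on intensity and the EPG distribution are not in the documents. Log-odds slopes per unit log EPG of 0, −0.5, −0.8 and −1.2 were taken. From 48 to 999 EPG, ln(999/48) = 3.04, so the odds of cure fall by a factor of 1, 4.6, 11 or 38. Log EPG was taken as normal, truncated at 48, with centre and SD (log 150, 1.1), (log 250, 1.3) or (log 600, 1.3). These put 95%, 84% or 64% of participants in the light stratum.

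**3. Simulation.** There were 10,000 runs per scenario: 282 randomised 1:1:1 in blocks of 6 within the two strata, each evaluable with probability 85/94, and intercepts set so that the marginal CRs equal the stated values. The table gives Wald power (%), unadjusted → adjusted for log EPG only.

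| CRs | Light share | slope 0 | −0.5 | −0.8 | −1.2 |
|---|---|---|---|---|---|
| 10% v 30% | 95% | 91.9→91.8 | 90.9→91.5 | 91.2→92.4 | 91.6→94.3 |
| 10% v 30% | 84% | 91.4→91.3 | 91.6→92.4 | 91.3→93.2 | 91.4→95.1 |
| 10% v 30% | 64% | 91.8→91.8 | 91.7→92.7 | 91.8→93.7 | 92.2→96.3 |
| 10% v 25% | 95% | 73.9→73.9 | 72.9→73.7 | 73.0→75.2 | 73.5→77.8 |
| 10% v 25% | 84% | 72.8→72.8 | 73.4→74.7 | 73.1→76.2 | 73.2→79.7 |
| 10% v 25% | 64% | 73.3→73.3 | 73.7→75.5 | 74.1→78.7 | 73.5→81.8 |

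The Monte Carlo standard error is 0.3 points near 92% and 0.4 near 75%. The largest gains are 96.3 − 92.2 = 4.1 points at 10% v 30%, and at 10% v 25% 79.7 − 73.2 = 6.5 points (84% light) and 81.8 − 73.5 = 8.3 points (64% light). A separate simulation with 84% light and log EPG as the sole covariate gave about 0 to +3.6 points at 10% v 30%, and −0.6 (within simulation error) to +5.8 at 10% v 25%.

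**4. Type I error.** Under equal CRs the unadjusted Wald test rejected in 3.5–4.8% of runs, and the test adjusted for log EPG alone in 3.7–4.3%. With likelihood-ratio tests the ranges were 4.8–5.6% unadjusted and 5.1–5.7% adjusted. Both analyses hold their level to within simulation error.

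**5. Stratum or log EPG.** Adjusting for the two-level stratum alone gained at most 0.1, 0.6 and 2.2 points at 95%, 84% and 64% light. Adding the stratum to log EPG changed power by at most 0.2 points. The useful information is in the continuous count.

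**6. Interval for the CR difference.** At 10% v 30% the Wald interval is 20 ± 1.96√(0.09/85 + 0.21/85) = 20 ± 11.6 points. In simulation the mean width was 23.1 points unadjusted. Standardised from a model with log EPG and the stratum, it was 23.3 at slope 0, then 22.8–23.0, 22.1–22.7 and 20.9–22.0 as the slope steepens. In that model the interval and the test disagreed in 0.3–1.4% of runs.

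**The case against.** The strongest reply is that this is a preference. Section 8.3 names one unambiguous model, the test is valid, and the primary comparison already has about 91% power. The benefit rests on a slope and a distribution that no document supplies; at slope −0.5 the primary comparison gains 1 point or less, and the 8-point figure comes from one corner of the grid. The choice between Wald and likelihood-ratio tests, on which the plan is silent, moves unadjusted power at 10% v 25% by about as much (73–74% v 75.5%, in simulations with somewhat different set-ups). Nor is an amendment free: version 2.0 is dated 6 May 2021, with the first participant planned for that month and the last out in August. All of this stands, and it limits the point to an optional improvement.

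It does not remove the point. The covariate is already collected, the loss if it is not prognostic is close to nil, and about 34 cures are expected in the two primary arms (8.5 + 25.5), enough for one added covariate.

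A reader might infer three stronger things, none of which the documents support:

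- That ignoring the stratification factor invalidates the test. It does not: its level is held in every scenario examined.
- That the trial is underpowered or the 75% misstated. The 90% reproduces, and the 75% cannot be called wrong when its base rate is not given.
- That the synopsis contradicts section 8.3. It only omits a word.

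**Conclusion.** The point holds as a suggestion to consider, with medium confidence. The planned analysis is correct but leaves a complete baseline covariate unused and names no interval on the scale used for planning.

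Adjusting for log EPG is worth about 0 to 4 points of power at 10% v 30%. At 10% v 25% it is worth about 0 to 6 points with 84% light infections, and up to about 8 with 64% light and the steepest slope. These ranges depend on the assumed slope, EPG distribution and 10% base rate. If intensity does not predict cure, there is no gain and the interval is about 0.2 points wider. The missing interval for the CR difference does not depend on any of these assumptions. A CI can of course be computed from the model; the gap is only that none is specified.

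**What to change.** Amend section 8.3, and align the synopsis, to read:

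> For each combination arm v albendazole, CRs will be compared by logistic regression on arm, adjusted for screening log EPG as a continuous covariate; the two-sided 5% test of the arm term is the test of superiority. The standardised (marginal) CR difference from this model with a robust 95% CI is the effect estimate; if test and CI disagree, the test governs. The unadjusted logistic regression is a sensitivity analysis.

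It would help to state whether the test is Wald or likelihood ratio.

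The stratum term is best left out. It adds almost nothing to log EPG, and with few heavier infections it often causes separation and so needs a fallback rule. A check for separation on pooled cures could not be made blind for ivermectin/albendazole v albendazole: section 4.4 leaves arm C open, so a pooled count would reveal the albendazole cures.

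If the sponsor keeps the unadjusted model, the minimum is to name a 95% CI method for the CR difference (for example Newcombe or Miettinen–Nurminen) and to add the word unadjusted to the synopsis.

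Cost: no new data or visits. Under section 9.1 the amendment needs the Sponsor/PI's signature and ethics committee approval, and submission to regulators if required; it should be complete before any outcome analysis. The tested parameter becomes a conditional odds ratio, which can occasionally disagree with the marginal interval; the wording above settles which governs.

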4.3.2 Microbiome stool collection

For microbiome analyses, *T. trichiura* positive samples as well as 100 STH negative controls (in up to 2 stool samples each at baseline and 14-21 days after treatment) will be analyzed. For this purpose, 1-2 g of freshly collected samples will be suspended in 15 mL of sterile phosphate buffer supplemented with 0.1% L-cysteine (PBSc) in a sterile 50 mL falcon tube. The tubes will be left for 5 minutes to let insoluble particles settle. 1 mL aliquots (up to 2 aliquots) of the supernatant will be transferred to sterile cryogenic vials, supplemented with 1 mL of 40% glycerol solution, and subsequently frozen (at -20°C) until shipment to Swiss TPH in Switzerland is arranged for subsequent molecular and microbiological

analyses. For the microbiome analysis additional data on height and weight of participants will be collected.

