4.3.6 Assessment of efficacy after treatment

The efficacy of the treatment will be determined 14-21 days post-treatment by collecting another two stool samples, which will be microscopically examined for *T. trichiura* using duplicate Kato-Katz thick smears. Participants will be considered cured if no *T. trichiura* eggs are found in the follow-up stool samples. Eggs per gram will be assessed by adding up the egg counts from the quadruplicate Kato-Katz thick smears and multiplying this number by a factor of six. Geometric and arithmetic mean egg counts will be calculated for the different treatment arms before and after treatment to assess the corresponding ERRs. At the end of the study all participants remaining positive for *T. trichiura* infection will be treated with the currently best recommended treatment of repeated doses of mebendazole (100 mg twice daily over 3 days).

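### Does the factor-of-six rule for eggs per gram need a provision for participants with only one follow-up stool?

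*Combined protocol and SAP*

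**What the plan says.** Section 4.3.1 asks for two stools per participant, each read as "duplicate Kato-Katz thick smears (41.7 mg each"), and applies the same approach at follow-up. That makes four slides per time point. Table 1 in section 4.6 repeats the two stools, and the statistical row of the synopsis defines cure from four-slide assays at 14-21 days.

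Sections 4.3.6 and 8.3 both obtain EPG by "adding up the egg counts from the quadruplicate Kato-Katz thick smears and multiplying this number by a factor of six". No other conversion is given. ERR compares mean EPG at follow-up with mean EPG at baseline. Section 4.3.6 plans it on two scales ("Geometric and arithmetic mean egg counts will be calculated for the different treatment arms"), and section 8.3 prints the geometric formula.

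At entry the full set is presupposed: "Having at least two slides of the quadruple Kato-Katz thick smears positive for" *T. trichiura*, with at least 48 EPG (section 5.2). For the primary analysis, section 8.3 uses the "available case population, which includes all participants with any primary end point data". Neither section says how EPG or ERR is handled when fewer than four follow-up slides are read.

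**The concern.** The factor depends on how much stool was examined. Two slides hold half the stool of four, so the same factor gives half the expected EPG. Baseline is normally complete because eligibility depends on it, so any shortfall falls mainly on follow-up. An error there has one direction: follow-up EPG too low, ERR too high.

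The plan also leaves room for incomplete sets. The primary analysis accepts any endpoint data, providing two follow-up stools is only something participants agree to, and section 5.4 keeps data collected before a withdrawal. Three treatments of a one-stool follow-up are then conceivable: multiply by six anyway, rescale to the slides read, or exclude. They give different ERRs, and the choice could be made after the data are seen. ERR is a secondary endpoint for both combination arms.

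**Working it through.** **1. The plan's own factor.** Input: 41.7 mg per slide (section 4.3.1). Factor = 1000 / (slides × 41.7).

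- Four slides: 1000/166.8 = 5.995, so the stated six reproduces.
- Two slides: 1000/83.4 = 11.99. One slide: 1000/41.7 = 23.98.
- The entry threshold fits: 48/6 = 8 eggs over four slides.

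**2. Does the text direct six for two slides?** No. Both statements of the rule name the quadruplicate smears. The wide wording, "available case population, which includes all participants with any primary end point data", is attached to the primary analysis, which compares cure and uses no conversion factor. The phrase "in up to 2 stool samples each at baseline and 14-21 days after treatment" in section 4.3.2 concerns which samples go to microbiome analysis and says nothing about egg counting.

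**3. Closed-form size if six were misapplied.** Let a share f have one stool and let CR be the cure rate. Halving EPG in the egg-positive members of that share multiplies the geometric mean by 2^(−f(1−CR)), ignoring the added 1. The rise in geometric ERR is (1−ERR) × (1 − 2^(−f(1−CR))). The documents give no f; the only attrition figure ("To account for a loss to follow-up of 10"%, section 8.2) is complete loss, a different quantity. Assumed f:

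| True ERR, CR | f = 5% | 10% | 20% |
|---|---|---|---|
| 50%, 10% | 1.5 | 3.0 | 5.9 |
| 90%, 30% | 0.24 | 0.47 | 0.92 |
| 97.4%, 62.5% | 0.03 | 0.07 | 0.13 |

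Entries are percentage points. The cure rates of 10% and 30% are the planning values in section 8.2; the last row is the earlier adolescent result in section 2; ERRs of 50% and 90% are assumed. For the arithmetic mean the rise is (1−ERR) × f/2: at f = 10%, 0.50 × 0.05 = 2.5 points and 0.10 × 0.05 = 0.5 points.

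**4. Simulation, every input assumed.** Baseline geometric mean 400 EPG, log-SD 1.2; follow-up multiplier 0.5 (low efficacy) or 0.15 (high), log-SD 1; truly cured 5% or 20%; day-to-day CV 100%; Poisson slides; section 5.2 entry criteria applied; one-stool status random; 1/n taken inside the exponent of the geometric mean. Geometric ERR at f = 10%:

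| Rule | Low | High | Difference |
|---|---|---|---|
| Sum × 6 on all | 70.01 | 95.01 | 25.0 |
| 24 × mean per slide read | 68.18 | 94.78 | 26.6 |
| Incomplete sets excluded (equals four slides for all) | 66.93 | 94.59 | 27.7 |

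Six versus rescaling: 70.01 − 68.18 = 1.83 and 95.01 − 94.78 = 0.23 points. At f = 5% and 20% the shifts are 0.9 and 3.4 (low), 0.1 and 0.4 (high). Six versus complete data: 70.01 − 66.93 = 3.08 and 95.01 − 94.59 = 0.42. Arithmetic ERR, six versus rescaling: 26.8 versus 23.0 (low), 81.4 versus 80.5 (high).

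A second simulation with other assumed distributions gave geometric shifts, six versus rescaling, of 2.6 (low) and 0.35 (high) at f = 10%. Its largest shifts, at low efficacy and f = 20%, were 4.9 geometric and 8.6 arithmetic.

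**5. Against sampling error.** The simulated SD of the geometric ERR at n = 85 is about 7.1 points (low) and 1.4 (high). Six versus rescaling: 1.83/7.1 = 0.26 and 0.23/1.4 = 0.16. Six versus complete data: 3.08/7.1 = 0.43 and 0.42/1.4 = 0.30.

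**6. Cure.** Zero times any factor is zero, so infection status does not depend on the factor. Reading fewer slides does miss some infections, but the simulated cure difference moves only from 26.92 − 7.28 = 19.64 points to 27.95 − 7.97 = 19.98 at f = 10%.

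**The case for a change.** The best case for a change is that the gap is real and closing it is cheap. Someone who withdraws after the first of two follow-up stools has data that section 5.4 says to keep, and no written way to turn them into EPG. Writing EPG as 24 times the mean count over slides read would leave complete data unchanged and fix the handling in advance. Section 4.4 says "Treatment arm A and B will be double blinded", which makes similar one-stool shares natural for that comparison, but the ivermectin/albendazole arm is open, so equal shares are less assured there and the error need not be conservative.

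It stands that no sentence covers the incomplete set. The rest carries less weight. EPG is a concentration, and the slide mass is in the protocol, so anyone converting two slides can see that six is the wrong multiplier.

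Nor is rescaling clearly the better rule. In the simulation it removes 1.83 of the 3.08 points of geometric bias, because fewer slides also yield more zeros. Excluding incomplete sets removes all of it when one-stool status is random, and on the arithmetic scale the two agree in expectation. The plan's silence therefore does not hide one obviously correct choice.

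For the open arm, suppose both arms behave like the low-efficacy case, with 10% one-stool follow-ups in one and none in the other. Misusing six then shifts the ERR difference by 3.08 points against an SD of √(7.1² + 7.1²) = 10.0, about 0.3 of a standard error.

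**Conclusion.** No change follows. The stated rule is correct for the four slides the plan specifies, and what is missing is a detail for incomplete follow-up sets that analysts would settle sensibly by rescaling or exclusion. Between those two defensible choices the geometric ERR differs, at an assumed 10% share, by 68.18 − 66.93 = 1.25 points in a low-efficacy arm and 94.78 − 94.59 = 0.19 points in a high-efficacy arm.

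Even the misuse of six would, at that share, move a secondary endpoint by 0.2 to 0.4 of a standard error. With equal shares it would narrow the contrast between moxidectin/albendazole and albendazole. The effect would be larger only with many incomplete follow-ups in a low-efficacy arm, and nothing in the documents indicates that.

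The factor arithmetic is certain. The sizes rest on an unknown one-stool share and on assumed egg-count distributions, so they show order of magnitude only. The equality of exclusion with complete data also requires that missing a stool is unrelated to egg output.

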Moxidectin, a macrocyclic lactone, has been an FDA-approved treatment for onchocerciasis and has shown promising efficacy when administering 8 mg in combination with albendazole (CR: 62.5%; ERR: 97.4%) against *T. trichiura* infections in adolescents [7]. A review of available data suggests that the high fat solubility, long half-life, intrinsic potency and high safety margin of moxidectin could allow this drug to be used at sufficiently high doses to safely remove ivermectin-resistant parasites. However, there is a need to explore whether moxidectin could reveal a benefit in the treatment of STH infections in settings where efficacy of ivermectin is low [8]. In this trial, we aim to evaluate if moxidectin in combination with albendazole is an efficacious treatment against *T. trichiura* in Côte d'Ivoire. Furthermore, this trial aims to substantiate the evidence of combined ivermectin/albendazole, since recent trial data suggests no major improvement against trichuriasis (observed CR of 13%).

The pharmacokinetic/-dynamic (PK/PD) characterization of a drug is essential to understand the response of the human body to a drug and vice versa, especially in populations that physiologically

differ from healthy adults. Physiological characteristics like mal- or undernutrition due to intestinal worms, such as *T. trichiura*, can potentially affect the PK of a drug [9, 10]. Age, sex, body weight but also the presence of certain enzymes in different populations are important contributors to the pharmacokinetic profile of a drug. Additionally, pharmacokinetic interaction may occur upon co-administration of different drugs.

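### As transcribed, the ERR equation in section 8.3 has 1/n outside the exponential, so it is not the geometric-mean ERR the text describes; coded literally at n = 85, a 5% fall gives 98.7%

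*Combined protocol and SAP*

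**What the plan says.** Section 8.3 defines the ERR by an equation. In the LaTeX form of the supplied text its numerator ends "1}{n} e^{\sum \log(EPG_{follow-up} + 1)} - 1", and the denominator is identical except that it uses baseline counts. In both, the fraction 1/n stands in front of the exponential.

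The sentence after the equation describes something else: "Geometric mean egg counts will be calculated for the different treatment arms before and after treatment to assess the corresponding ERRs". Section 4.3.6 and the statistical part of the synopsis also describe the ERR in words only, naming both kinds of mean: "Geometric and arithmetic mean egg counts will be calculated for the different treatment arms". No other section gives an ERR equation.

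The interval method applies to this statistic: "Bootstrap resampling method with 5,000 replicates will be used to calculate 95% confidence intervals (CIs) for ERRs and the difference between the ERRs".

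**The concern.** A geometric mean with a +1 offset is exp((1/n) Σ log(EPG + 1)) − 1, with 1/n inside the exponent. With 1/n outside, exp(Σ log(EPG + 1)) is the product of all n values. The equation therefore contradicts the sentence that explains it.

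The ERR serves secondary objectives a to c in section 3: moxidectin/albendazole and ivermectin/albendazole, each against albendazole alone, and the co-infecting species. An analyst who follows the equation gets values near 100% for almost any reduction, and those values depend on the number of participants. One who silently corrects it departs from the written plan. The result could not be set beside the earlier moxidectin/albendazole result in section 2 ("CR: 62.5%; ERR: 97.4" per cent), although that section does not say which mean the earlier ERR used.

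**Working it through.** **Inputs.** n = 85 evaluable and 94 recruited per arm (8.2). Cure rates of 10%, 13% and 30% (8.2: "We estimate a true CR of 10% for albendazole monotherapy and 30% for combination moxidectin/albendazole"; the 13% is the earlier ivermectin/albendazole result). Minimum baseline count (5.2: "infection intensities of at least 48 EPG"). The plan states no ERR computed from this equation, so there is no figure to reproduce.

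**Step 1: what the equation reduces to.** Let P0 and P1 be the products of (EPG + 1) at baseline and follow-up. As transcribed,

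ERR = 1 − (P1/n − 1) / (P0/n − 1).

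Every participant has at least 48 EPG at baseline, so P0/n ≥ 49^85 / 85 ≈ 10^141.7. The −1 terms are negligible and the two factors 1/n cancel. With r the ratio of the geometric means of EPG + 1,

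ERR ≈ 1 − P1/P0 = 1 − r^n.

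**Step 2: a small fall.** For a 5% fall, r = 0.95:

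- n = 85: 1 − 0.95^85 = 98.7%
- n = 94: 1 − 0.95^94 = 99.2%
- n = 30: 78.5%; n = 10: 40.1%

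The geometric-mean form gives 5.0% to 5.1% at every n (baseline geometric means of 48 to 5,000 EPG tried). The dependence on n matters for objective c, where the co-infected subgroups will differ in size.

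The fall that would be reported as 97.4% is 1 − 0.026^(1/n): 4.2% at n = 85 and 3.8% at n = 94.

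**Step 3: the cure rates in 8.2.** Assume a uniform baseline b, cured participants at 0 EPG and uncured participants unchanged. Then the correct ERR is 1 − [(b + 1)^(1−CR) − 1]/b, and the transcribed equation falls short of 100% by (b + 1)^(−85·CR).

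| Baseline (EPG) | Correct, CR 10% | Correct, CR 13% | Correct, CR 30% | As transcribed |
|---|---|---|---|---|
| 48 | 32.9% | 40.5% | 70.3% | 100% in all three |
| 300 | 43.6% | 52.6% | 82.2% | 100% in all three |
| 1,000 | 49.9% | 59.3% | 87.5% | 100% in all three |

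The largest shortfall is 49^(−8.5) ≈ 4 × 10^−15. At 48 EPG, a true difference of 70.3 − 32.9 = 37.4 points between the primary arms would show as zero.

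**Step 4: the bootstrap interval for the difference in ERR.** Take 8 v 25 cured of 85 at 48 EPG, with 5,000 replicates and each participant's baseline and follow-up kept paired. The uncured have mean log change 0 and an assumed SD. Figures are medians over 40 simulated data sets, in percentage points.

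| SD of log change in uncured | As transcribed | Correct form |
|---|---|---|
| 0 | 0 to 0.0009 | 16.9 to 59.2 |
| 1.0 | upper limit about 0.6 (range 0.3 to 1.5) | 12.8 to 65.8 |
| 1.5 | upper limit about 540 (range 92 to 2,650) | 8.6 to 73.3 |

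At 300 EPG the transcribed upper limits are 0.000004, 0.0003 and 0.09 points.

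The SD 0 case can be checked by hand. With k cured in a resample, the transcribed ERR falls short of 100% by 49^(−k). The 2.5th percentile of k in the weaker arm is 3, and 49^(−3) is 0.00085 points.

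With only 2 cured in the weaker arm, a resample contains no cured participant with probability (83/85)^85 ≈ 13%, and its ERR is then 0. The interval runs from about 0 to 100 points, against 42.1 to 76.0 for the correct form.

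**The case against.** The strongest objection is that the text was read from a PDF by a program. A small fraction in an exponent could have been lowered to the baseline, and the same misreading could have hit numerator and denominator alike. If so, the plan contains no error. This stands as a limit on certainty, and it is why the first step is to look at the original page.

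Second, the intent is not in doubt. The adjacent sentence names geometric means, and the log(EPG + 1) with a trailing −1 fits only an offset geometric mean. A literal coding would probably be noticed: the baseline term is about 10^142 or more, and at n = 85 the product overflows double precision once the geometric mean of EPG + 1 exceeds about 4,232. This lowers the likelihood of harm. It does not make the equation right, and a pre-specified formula should work as written.

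Third, section 4.3.6 and the synopsis also promise arithmetic means ("Geometric and arithmetic mean egg counts will be calculated for the different treatment arms before and after treatment to assess the corresponding ERRs"). ERRs built on those do not use this equation, so they would remain usable and would expose an absurd geometric value. That is correct. It does not repair the only formula given, and section 8.3 itself names only the geometric mean.

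Fourth, the simulations rest on assumptions from outside the plan, and the upper limit at SD 1.5 is unstable, as its range shows. They illustrate how the interval behaves and are not a forecast. The core result, 1 − r^n, needs none of them.

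**Conclusion.** The concern holds for the text as supplied. The equation in 8.3 does not give the ERR that 8.3 describes, and nothing else in the plan corrects it. Followed literally, a 5% fall reads as 98.7% (n = 85) or 99.2% (n = 94), and the arms cannot be told apart at the planned cure rates. The interval for the difference is uninformative: close to zero width in most settings tried, and extremely wide when the weaker arm has little effect or individual changes vary widely.

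The table of ERRs assumes a uniform baseline (48, 300 or 1,000 EPG) and no change in the uncured. The intervals also assume the SDs shown and, for the weak-effect case, 2 cured. None of these comes from the documents.

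This is most likely a notation slip with a clear intended meaning, confined to the secondary ERR analyses. It should be fixed, with moderate confidence until the original page has been checked.

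**What to change.** Check where 1/n stands on the original page of section 8.3. If it is in the exponent, nothing needs to change. If it is as transcribed, replace the equation by

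ERR = 1 − [exp((1/n) Σ log(EPG_follow-up + 1)) − 1] / [exp((1/n) Σ log(EPG_baseline + 1)) − 1]

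and run the 5,000-replicate bootstrap on that statistic.

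The cost is one corrected equation. Data collection, sample size and the primary analysis do not change. Section 9.1 requires the modification to be documented in writing and, if it is handled as an amendment, submitted to the ethics committee.
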